5.5.1.4. DENV-associated signs and symptoms

To evaluate the antiviral effect of JNJ-64281802 as early treatment among HHC who have evidence of DENV infection at baseline, descriptive analyses will be done on the DENV-associated signs and symptoms.

DENV-associated signs and symptoms are defined as the reported solicited adverse events (Table 3). Tabulations will be provided showing the proportion of subjects per reported adverse events.

Time to end of end of DENV Infection-associated AEs will be defined as the time between the minimum of all start dates and the maximum of all end dates+1 day and will be censored if there are still signs & symptoms present at Day 28. Time to end of end of DENV Infection-associated AEs will be analyzed using Kaplan-Meier (KM) estimates. A summary table including number of participants included in the analysis, number of participants censored, 25th and 75th percentiles, and median time-to-event, with 95% CIs based on log-log transformation method, will be presented. The data will be presented graphically using the Kaplan-Meier estimate of the survival function by study drug.

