- the proportion of incident DENV infections that become symptomatic in the primary study population was hypothesized to be 20% during the 28-day dosing period;
- the proportion of prevalent DENV infections that become symptomatic in the secondary study population was hypothesized to be 10% during the 28-day dosing period.

The simulations are fully described in the modelling and simulation report (MSR)², which also contains the simulation programs.

The simulations showed that at the FA and under the protocol assumptions, the study design results in at least 85% power for the primary objective assessed for the HDR and at least 80% power for the key secondary analysis, irrespective of the PE LDR. If the PE LDR is at least 90% of the PE HDR, the study also has at least 80% power for the primary objective assessed for the LDR and has at least 90% power for the key secondary objective. The expected recruitment of the study ranges from 1250 (assuming the PE of LDR is 0%) to 1850 (assuming the PE of LDR is equal to the PE of HDR, ie. 75%). If the PE of LDR is 50% of the PE of HDR, the expected study recruitment is 1455. If 1.5 eligible HHC can be recruited/index case, this requires the identification of nearly 1000 index cases

The study design is robust to minor deviations from the protocol assumption. If the PE of HDR is 5 percentage points lower than the protocol assumptions, the power for the primary analysis (HDR) is maintained to \geq 77%. If the incidence or prevalence of (symptomatic) DENV infections is different from protocol assumptions, the proposed design generally maintains a power for the primary analysis \geq 80% and for the key secondary analysis \geq 75%. However, if incidence of (symptomatic) DENV infections is lower than expected the total study recruitment will be increased.

The study ended prematurely when 21 laboratory confirmed dengue infections between baseline and last day of dosing (+1 day) were observed in the primary analysis population and 14 symptomatic dengue infection between baseline and last day of dosing (+1 day) were observed in the completed study population.

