5.4. Secondary Endpoint(s) Analysis

5.4.1. Key Secondary Endpoint(s)

5.4.1.1. Definition of Endpoint(s)

The key secondary endpoint is defined as presence or absence of laboratory-confirmed symptomatic DENV infection between baseline and last day of dosing + 1 day. Laboratory-confirmed symptomatic DENV infection is defined as having at least 2 solicited systemic AEs, of which at least one is a most common dengue symptom (see Table 3), lasting for ≥ 1 day and

occurring within a +/-2 days time window around the positive PCR or NS1 test. If a sample is missing and the next or prior available sample is positive for a DENV infection, the missing sample will be considered as positive for DENV infection as well. Consequently, solicited AEs observed within +/-2 days around the scheduled missing sample date will be considered as well as a confirmation of a symptomatic DENV infection.

Table 3: Solicited systemic AEs

- Retro-orbital pain*	- Fever*	- Fatigue	- Vomiting
- Abdominal pain	- Headache *	- Myalgia *	- Diarrhea
- Arthralgia*	- Nausea	- Loss of appetite	- Rash *

^{*} Most common dengue symptom

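### The Kaplan-Meier for time to end of dengue-associated AEs covers only contacts who had an AE, so it cannot show symptoms prevented by early treatment

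*SAP*

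**What the plan says.** The secondary study population (SAP Section 4) consists of dosed contacts with a positive RNA or NS1 result at baseline but no dengue signs or symptoms at that point. SAP 5.5.1.4 uses it to describe the antiviral effect of early treatment on signs and symptoms, in two ways.

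The first is a table: "Tabulations will be provided showing the proportion of subjects per reported adverse events".

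The second is a time-to-event variable: "Time to end of end of DENV Infection-associated AEs will be defined as the time between the minimum of all start dates", ending one day after the latest end date. It "will be censored if there are still signs & symptoms present at Day 28". It is summarised by Kaplan-Meier, with quartiles and a curve by study drug. No other rule on scoring or censoring is given.

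The events that count are broad: "DENV-associated signs and symptoms are defined as the reported solicited adverse events (Table 3"). One entry from the list of 12 is enough.

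SAP 1.1 places this objective among those that might be analysed, depending on the unblinded primary and secondary results, to generate hypotheses.

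**The concern.** The population is symptom-free at baseline by definition, so some of it will stay symptom-free. For a drug given as early treatment, that is the best possible result. Such a participant has no start date and no end date, and the SAP assigns no duration, event or censoring time. A participant who leaves before Day 28 with an AE still open also has no rule.

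Taken at its word, the definition gives a value only to participants who developed an AE after randomisation. If the drug affects who develops one, the participants under the curves are no longer comparable between arms. A drug that prevents episodes could show no difference in median duration. A drug that mainly prevents short episodes could show a longer median. Because the analysis depends on unblinded results, any missing rule would also be filled in after the allocation is known.

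**Working it through.** **1. The two time-to-end endpoints side by side.** In SAP 5.5.1.3, time to end of detectable RNA is counted from Day 1, and a participant whose last result is still detectable is censored at the last available sample. In SAP 5.5.1.4 the count starts at the first AE, and the only censoring is for symptoms present at Day 28. The RNA endpoint has a common origin and a general censoring rule; the symptom endpoint has neither.

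**2. Is 10% a real working figure in the plan?** SAP Section 3 says "the proportion of prevalent DENV infections that become symptomatic in the secondary study population was hypothesized to be 10" per cent. The other inputs from that section are: 20% infected at recruitment, 20% unevaluable, 7.5% incidence, 20% of incident infections symptomatic, efficacy of 75% (infection) and 72.5% (symptomatic), and targets of 36 infections and 24 symptomatic infections. Allocation is 1:1:1.

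- Infections per recruit: r1 = 0.80 × 0.80 × 0.075 × mean over arms of (1 − PE) = 0.048 × that mean.
- Symptomatic infections per recruit: r2 = 0.80 × (0.80 × 0.075 × 0.20 + 0.20 × 0.10) × mean over arms of (1 − symptomatic PE) = 0.0256 × that mean.
- N = larger of 36/r1 and 24/r2.

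| LDR efficacy | 36/r1 | 24/r2 | SAP figure | Difference |
|---|---|---|---|---|
| 0% | 1,000 | 1,236 | 1,250 | −1.1% |
| half of HDR | 1,200 | 1,471 | 1,455 | +1.1% |
| equal to HDR | 1,500 | 1,815 | 1,850 | −1.9% |

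The stated recruitment is reproduced within 2%, so the 10% is a working input of the plan.

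**3. What the 10% measures.** It feeds the target for symptomatic infection. SAP 5.4.1.1 defines that as "having at least 2 solicited systemic AEs, of which at least one is a most common dengue symptom", lasting at least a day and "occurring within a +/-2 days time window around the positive PCR or NS1 test". Entry to the 5.5.1.4 curve needs only one solicited AE of any kind. The complement, 90%, is therefore the share not meeting the stricter definition. It is not the share with no AE.

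**4. Range for the unscored share on placebo.** Let q be the share of contacts not meeting the symptomatic definition who still report at least one solicited AE. The documents do not give q, so it is varied here. Unscored share = 0.90 × (1 − q):

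- q = 0: 90%
- q = 0.10: 81%
- q = 0.25: 67.5%
- q = 0.50: 45%

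At q = 0 on HDR, if the 72.5% efficacy stated for the complete study population also held in this subgroup (an assumption), the share would be 1 − 0.10 × 0.275 = 97%. The unscored share would then differ between arms because the drug works.

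**5. Can the curve mislead?** Episode lengths here are assumed: gamma with shape 4 and scale 1.5, rounded up, plus one day, median 7 days, with 10% of placebo contacts having an episode. In a simulation, preventing 72.5% of episodes at random lowers the share with an episode from 10.0% to 2.8%, yet the median among those with one is 7 days in both arms. If the prevented episodes are the shortest ones, the share again falls to 2.8% but the drug-arm median rises to 11 days. This shows that reversal is possible, not that it is likely.

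**The case against.** The strongest reply concerns weight. The analysis is optional, descriptive and carries no between-arm test. Prevention is visible elsewhere. The table in SAP 5.5.1.4 gives proportions per AE. The key secondary endpoint is binary, includes baseline-infected contacts, counts those without symptoms as non-events and adjusts for baseline infection. The Kaplan-Meier table must also show how many participants are included, so a reduced denominator would be seen. Duration among the symptomatic is a legitimate quantity in itself.

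Most of this stands, and it keeps the point small. Some gaps remain. The table is per AE and does not give the proportion with any solicited AE. Protocol 9.4.4.1 plans that proportion, but for the safety population. The key secondary analysis is gated on the primary result and gives no separate estimate for baseline-infected contacts. None of these changes what the curve and median by study drug appear to say.

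It is also fair that the SAP is silent on excluding participants without an AE, and that output shells sit in a separate document not available here. But neither exclusion nor zero-scoring is written down, and only participants with an AE have the two dates the definition needs.

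A reader might infer that, by the SAP's own figure, about 90% of baseline-infected contacts never report an AE. The documents do not support that. The 10% is a planning assumption for a stricter definition, so 90% is an upper limit on placebo under that assumption. Nor should counts per arm be built from 1,250 to 1,850 recruits: the study stopped with 21 infections and 14 symptomatic infections, against targets of 36 and 24.

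**Conclusion.** The point holds as a minor one. As defined, the endpoint has no value for baseline-infected contacts without a solicited AE and no censoring rule for those who leave before Day 28 with an open AE. The Kaplan-Meier by study drug is then duration in a group selected after randomisation. It cannot show prevented symptoms, and it may mislead about early treatment.

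The unscored share is not known from the documents. On placebo it is at most about 90% under the 10% planning assumption, and about 45% if half of the contacts outside the symptomatic definition report at least one solicited AE. SAP Section 1 reports 14 symptomatic infections in the complete study population, so at most 14 confirmed symptomatic cases across three arms could come from this group. Any other entries to the curve would be solicited AEs outside that definition.

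A reader might go further and conclude that the result would be biased against the drug. That direction rests only on assumed episode lengths and is not established.

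**What to change.** In SAP 5.5.1.4, for all participants in the secondary study population, report by arm:

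- the proportion with any solicited AE; and
- the number of days with at least one solicited AE over Days 1-28, with zeros included, shown as mean and distribution because the median may be 0.

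Keep the Kaplan-Meier only as duration among participants with an AE, label it as not a randomised comparison, and censor at last contact those who leave with an open AE.

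Time from first intake should not replace the present definition. It would mix onset with duration, so a single late, short AE would score as a long time.

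The cost is a few sentences and one derived variable from diary data already collected. The downside is a variable with many zeros.

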5.5.1.5. DENV Infections in Follow-up

Individual data on DENV Infections observed in follow-up period will be provided.

5.6. Safety Analyses

All safety analyses will be based on the safety analysis set and actual intervention received, unless otherwise specified.

For all continuous safety variables, descriptive statistics by intervention group will include: N, mean, standard deviation, median, minimum, and maximum. Categorical variables will be summarized by intervention group using frequency counts and percentages.

5.6.1. Extent of Exposure

The number and percentage of participants who received study intervention will be summarized by study intervention group.

Study intervention duration is defined as:

date of last dose of study intervention – date of first dose of study intervention +1 (including days off study intervention).

Duration of intervention will be summarized in the following duration categories:

```
[<1 week, 1-<2 weeks, 2-<3 weeks, 3-<4 weeks, 4 weeks].
```

Total dosing days of intervention is defined as:

total number of days that study intervention was taken by the participant (excluding days off study intervention).

Compliance is defined as:

Compliance (%) = 100 x Total dosing days of intervention/Study intervention duration

Study intervention compliance will be summarized descriptively. In addition, compliance will be summarized in the following categories:

- o The number of full compliant participants,
- The number of participants for which >= 1 LD was missed,
- o The number of participants for which >= 1 MD was missed,
- o The number of participants with 2 consecutive missed MDs,
- The number of participants with > 1 missed MDs within a week.

Exposure and compliance will be given for each of the following population: safety, primary, secondary and complete study population.

5.6.2. Adverse Events

The verbatim terms used in the CRF by investigators to report adverse events will be coded using the Medical Dictionary for Regulatory Activities (MedDRA version 25.0). Any AE occurring at or after the initial administration of study intervention until the last study-related activity, or until

the participant has been deemed lost to follow-up after demonstration of due diligence of follow-up efforts will be considered as treatment emergent. If the event occurs on the day of the initial administration of study intervention, and either event time or time of administration are missing, then the event will be assumed to be treatment emergent (TE), unless the AE is reported based on a baseline laboratory result, in which case the AE will be assigned to the screening phase. The list of coded AE terms that are based on a laboratory result is included in appendix 8 (section 6.8). If the event date is recorded as partial or completely missing, then the event will be considered as treatment emergent unless it is known to be prior to the first administration of study intervention based on partial onset date or resolution date. All reported adverse events will be included in the analysis. For each adverse event, the number and percentage of participants who experience at least 1 occurrence of the given event will be summarized by intervention group.

Separate tables and participants listings will be created for solicited (see Table 3) and unsolicited adverse events, showing the results by study intervention group.

Summary tables by study intervention group will be provided for adverse events by phase (Prophylactic Dosing, Follow-up and both phases combined):

- AEs
- Serious AEs (SAEs)
- AEs leading to discontinuation of study intervention/termination of study participation
- AEs by toxicity grade assigned by the investigator, based upon protocol appendix 9.
- AEs by relationship to study intervention
- AEs leading to dose interruption of study intervention

In addition to the summary tables, participants listings will be provided for participants who:

- Had SAEs
- Had AEs leading to discontinuation/interruption of study intervention or termination of study participation

A listing of participants who died will be provided.

5.6.3. Additional Safety Assessments (if applicable)

5.6.3.1. Clinical Laboratory Tests

Clinical laboratory tests will be displayed for the participants included in the safety analysis set and will be restricted to the laboratory tests as required by Section 10.8 appendix 8 of the protocol, with exception of the differential WBC counts for which the level of data cleaning was deemed insufficient (neutrophils, lymphocytes, monocytes, eosinophils and basophils). The analysis of laboratory data will be done at the level of standardized values and units.

As for some laboratory tests local labs are used for the value determination, pooled results over the different labs will only be provided on the categorical results, ie. based on the normal limits or

based on toxicity grades. The laboratory reference ranges from the lab where the samples were analyzed will be used to determine the laboratory abnormalities or toxicity grades.

Toxicity grades will be determined according to the Table for Laboratory Abnormalities as shown in the original protocol (dated 09 November 2021), or, if not available, as shown in protocol amendment 3 (dated 19 July 2023), Section 10.9 Appendix 9 and will be attributed to the baseline and postbaseline values. In case no toxicity grades are defined for a test, the abnormalities (below/above normal ranges) will be used.

Postbaseline abnormalities will be compared with their corresponding baseline result:

- For toxicity grades, treatment emergence (TE) will be concluded if the postbaseline grade is worse than the baseline grade.
- For abnormalities based on normal range and/or criteria: If the postbaseline value is above the upper limit and the baseline value is below the upper limit (eg, Normal or Low), then the postbaseline abnormality will be considered TE. The same applies to the postbaseline value being below the lower limit with the baseline value being above the lower limit (eg, Normal or High).
- If the baseline value is missing, a postbaseline abnormality will always be considered as TE.
- The worst TE grade/abnormality will be determined. The worst TE toxicity grade is the highest grade reached. For non-graded abnormalities, the 'low' and 'high' classes are equally worse, both will be considered as worst abnormality.

A summary table will show the number and percentage of participants per TE abnormality. Shift summaries from baseline laboratory value to the worst toxicity grade/abnormality in chemistry and hematology tests will be presented by intervention group.

Descriptive statistics and mean \pm SE graphs by lab and by study intervention will be presented at scheduled time points on actual values and changes from baseline for chemistry, hematology, and urinalysis (pH and specific gravity) laboratory tests restricted to the laboratory tests for the labs in which at least 100 participants were analyzed.

In addition to the above tables, summary listings will be provided for all participants with treatment-emergent abnormal laboratory values of at least grade 2, or with reported clinically significant laboratory results whether treatment-emergent or not. This listing will include all other time points for the corresponding participant/parameter.

5.6.3.2. Vital Signs and Physical Examination Findings

Continuous vital sign parameters including pulse and blood pressure (systolic and diastolic) will be summarized at each scheduled assessment time point. Change from baseline will be summarized by intervention group. Descriptive statistics (mean, standard deviation, median, minimum and maximum) will be presented.

According to protocol, vital signs parameters should have been collected in supine position. However, if these are not available, available standing or semi-recumbent position can be used.

Abnormality grades will be determined according to the Division of Acquired Immunodeficiency Syndrome (DAIDS) Table for Grading the Severity of Adult and Pediatric Adverse Events, Version 2.0 (DAIDS 2017) and supplemented where values were absent (see Table 6) and will be attributed to the baseline and postbaseline values.

Table 6: Graded Abnormal Vital Signs

Vital Sign	Mild (Grade 1)	Moderate (Grade 2)	Severe (Grade 3)
Pulse (bpm)			
Tachycardia	>100-115	>115-130	>130
Bradycardia	50-54	<50-45	<45
Systolic blood pressure (mmHg)			
Hypertension (Systolic)	141-150	>150-155	>155
Hypotension (Systolic)	85-89	80-<85	<80
Diastolic blood pressure (mmHg)			
Hypertension (Diastolic)	91-95	>95-100	>100

Postbaseline values will be compared with their corresponding baseline values.

- TE will be concluded if the postbaseline grade is worse than the baseline grade.
- If the baseline value is missing, a postbaseline abnormality will always be considered as TE.
- The worst TE grade will be determined. The worst TE toxicity grade is the highest grade reached.

A summary table will show the number and percentage of participants per emergent abnormality. In addition, shift summaries from baseline value to the abnormality will be presented by intervention group.

A listing of abnormal individual participant vital signs values from scheduled and unscheduled time points will be provided. This listing will include all other time points for the corresponding participant/parameter

All abnormal physical examination results will be listed, including clinical significance specifications if/as provided.

5.6.3.3. Electrocardiogram

The ECG parameters as measured by the central monitoring that will be analyzed are heart rate, PR interval, RR interval, QRS interval, QT interval, and corrected QT (QTc) interval using the following correction methods: Bazett's formula (QTcB) and Fridericia's formula (QTcF)^{3,4}.

QTcB and QTcF values will be used as reported by central ECG lab, they will not be recalculated.

If ECG measurements are repeated at a visit, only the first measurement will be considered in the 'Visit' ECG result. The repeat measurements can be used for the worst TE grade/abnormality as explained below.

Descriptive statistics (mean, standard deviation, median and ranges) of actual ECG parameters and change from baseline will be summarized by intervention group at each scheduled time point.

The actual values for HR, PR, QRS, QTcB and QTcF and the changes from baseline for QTcB and QTcF will be categorized into abnormalities using the boundaries defined in Table 7.

Table 7:	Criteria for Abnor	rmal QTc Values and Ch	anges from Baseline

Abnormality class and label	ECG parameter			
	HR (bpm)	PR (ms)	QRS (ms)	QTcB and QTcF
Abnormalities for actual value	s		·	
Low	< 45	< 110	-	-
High	≥ 120	≥ 220	≥ 120	-
]450, 480] ms M/F (*)				> 450 - ≤ 480
]450, 480] ms M/F (*)				> 470 - \le 480
]480, 500] ms				> 480 - ≤ 500
> 500 ms				> 500
Abnormalities for change from	baseline		·	
]30, 60] ms				> 30 - ≤ 60
> 60 ms				> 60

^(*) The boundaries for QTcB and QTcF abnormalities are different for males and females, but the same abnormality label will be used.

No abnormalities will be defined for uncorrected QT, but uncorrected actual QT values >500 ms will be flagged and only shown in listings. Actual QTc values ≤ 450 ms are considered as normal, as well as all changes ≤ 30 ms.

Postbaseline abnormalities will be compared with their corresponding baseline result:

- TE will be concluded if the postbaseline value is above the upper limit and the baseline value is below the upper limit (eg, Normal or Low). The same applies to the postbaseline value being below the lower limit with the baseline value being above the lower limit (eg, Normal or High).
- If the baseline value is missing, a postbaseline abnormality will always be considered as TE.
- When changes from baseline are concerned (QTcB/QTcF), abnormality classes are always TE, per definition.
- The worst TE grade/abnormality by phase will be determined. For non-graded abnormalities, the 'low' and 'high' classes are equally worse, both will be considered as worst abnormality.

A summary table will show the number and percentage of participants per emergent abnormality for the prophylactic phase. A cross-tabulation of the worst abnormality versus baseline will be presented by intervention group.

A tabulation of the worst QT/QTc change versus baseline will be presented by study intervention.

A listing of clinically relevant ECG abnormalities from scheduled and unscheduled time points will be provided. This listing will include all other time points for the corresponding participant/parameter.

Subgroup Analyses

Subgroup analysis for the participants included PK substudy will be performed.

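### The ECG treatment-emergence rule applies one upper limit to QTc values that Table 7 puts in ordered bands, so worsening from an already raised baseline can be missing from the emergent counts

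*SAP*

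**What the plan says.** SAP 5.6.3.3 has three TE provisions for ECG.

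- For actual values: "TE will be concluded if the postbaseline value is above the upper limit and the baseline value is below the upper limit". The qualifying baseline is illustrated as Normal or Low, and a mirror rule covers the lower limit.
- For a missing baseline: "If the baseline value is missing, a postbaseline abnormality will always be considered as TE".
- For QTc changes: "When changes from baseline are concerned (QTcB/QTcF), abnormality classes are always TE, per definition". The change classes are >30 to 60 ms and >60 ms.

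Table 7 gives HR, PR and QRS Low and/or High cut-offs. QTcB and QTcF have no Low or High entry. They have three ordered bands of actual value, and the lowest band starts at 450 or 470 ms depending on sex: "The boundaries for QTcB and QTcF abnormalities are different for males and females, but the same abnormality label will be used". The text also states: "Actual QTc values ≤ 450 ms are considered as normal, as well as all changes ≤ 30 ms".

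The main ECG output counts emergent findings only: "A summary table will show the number and percentage of participants per emergent abnormality for the prophylactic phase". A second output is less specific: "A cross-tabulation of the worst abnormality versus baseline will be presented by intervention group".

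Elsewhere the SAP handles ordered categories differently. In 5.6.3.1: "For toxicity grades, treatment emergence (TE) will be concluded if the postbaseline grade is worse than the baseline grade". SAP 5.6.3.2 uses the same worse-than-baseline rule for vital signs. Protocol 9.4.4.1 plans the percentages of participants with QTc above 450, 480 and 500 ms, with no condition on baseline.

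**The concern.** A rule built on a single limit suits a parameter that is simply low, normal or high. QTc is classed by degree, and movement between bands is what a reader of a QTc table looks for. Under a single-limit rule, a participant who starts above the first limit has already failed the baseline condition, so no later band, including >500 ms, can be emergent in the actual-value rows. Participants with the highest starting QTc are then the ones whose worsening can go uncounted. Because the summary table is restricted to emergent abnormalities, the >480 to 500 and >500 ms rows could be lower than the number of participants who newly reached those values.

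**Working it through.** This is a check of a classification rule, so the plan has no figure to reproduce. The inputs are the Table 7 bands, the TE provisions and the change classes, all from SAP 5.6.3.3. The text does not print which sex goes with which lower boundary, so both are shown.

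**Rules applied**

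- Single limit L (450 or 470 ms): TE if the post-baseline value is above L and the baseline is not.
- Boundary of the band entered (480 or 500 ms for the upper bands): TE if the post-baseline value is above that boundary and the baseline is not.
- Change class: rise = post-baseline minus baseline; TE if above 30 ms.
- Worse class: TE if the post-baseline band is higher than the baseline band.

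| Baseline to post-baseline (ms) | Rise | Single limit 450 | Single limit 470 | Boundary of band entered | Change class | Worse class |
|---|---|---|---|---|---|---|
| 455 to 505 | 50 | not TE | TE | TE | >30 to 60, TE | TE |
| 475 to 502 | 27 | not TE | not TE | TE | none | TE |
| 485 to 505 | 20 | not TE | not TE | TE | none | TE |
| 455 to 484 | 29 | not TE | TE | TE | none | TE |

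**Which participants escape both rules under the single-limit reading (whole ms)**

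- New value above 500 ms: the post-baseline value is at least 501. A rise of at most 30 needs a baseline of at least 501 − 30 = 471. The baseline must also be at most 500. The range is therefore 471 to 500 ms, the same for both lower boundaries.
- New value in the >480 to 500 band: the post-baseline value is at least 481, so the baseline is at least 481 − 30 = 451 and at most 480. With the 450 ms limit the range is 451 to 480 ms; with the 470 ms limit it is 471 to 480 ms.

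**Which participants are flagged only as a change**

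From 455 ms, any value above 500 ms is a rise of more than 45 ms. Values of 501 to 515 ms fall in the >30 to 60 class and values of 516 ms or more in the >60 class. With the 450 ms limit such a participant is TE as a change but absent from the TE >500 ms row.

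**Which reading the text supports**

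The SAP does not say which boundary is the upper limit for QTc. The Normal or Low example favours a single limit of normal, because a baseline in the first QTc band is neither. The wording also closely follows the rule that SAP 5.6.3.1 reserves for laboratory tests without grades, where it stands beside a separate rule for graded tests. The ECG section has no such second rule.

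**The case against.** The strongest reply has four parts.

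**Large rises are still flagged.** A reader might infer that a participant who goes from 455 to above 500 ms is not counted as TE at all. The documents do not support that. The change-class provision makes every such rise TE, and for the sex with the 470 ms boundary 455 ms is below the limit, so the actual value is TE too. Nor is everyone with a raised baseline affected: someone who stays in the same band would not be TE under the worse-class rule either. This part stands and sets the size of the point.

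**The limit could be band-specific.** If the upper limit means the boundary of the band entered, all four examples are TE. The SAP neither states nor excludes this. It weakens any claim that the rule was meant to omit these values, but two programmers could still produce different counts.

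**Other outputs may show the shift.** The cross-tabulation against baseline, the tabulation of worst QT/QTc change and the listing of clinically relevant abnormalities all remain. The protocol's unconditional percentages are not withdrawn in SAP Appendix 2, and the SAP is to be read with the protocol. This stands in part. The SAP defines only a worst TE abnormality, so it is unclear whether the cross-tabulation is limited to emergent findings, and SAP 5.6.3.3 does not restate the percentages.

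**Few participants may be involved.** Contacts are healthy, a history of Torsades de Pointes risk factors excludes them, and the protocol background reports no repolarization effect in the first-in-human study. Main-study completers have one scheduled on-treatment ECG (Day 28); only the PK substudy of 30 to 40 participants adds Day 3. This makes a small count likely but does not settle it, since the eligibility criteria set no numeric QTc limit.

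**Conclusion.** The point holds in a limited form. Read as written, SAP 5.6.3.3 prevents a TE actual-value QTc finding in anyone whose baseline is above the first limit. For large rises the loss is confined to the actual-value row, because the change class is still TE. For rises of 30 ms or less that cross 480 or 500 ms from a raised baseline, there is no TE flag at all. The emergent-only summary can therefore undercount new QTc values above 480 and 500 ms.

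This rests on reading the upper limit as a single limit of normal. If a band-specific boundary was intended, the defect is one of specification only, and the same sentence would cure it. The number of participants affected cannot be derived, because the documents give no baseline QTc distribution. The cross-tabulation may show the same shifts, so the information is not necessarily lost from the report; it is the emergent count that is unreliable.

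**What to change.** In SAP 5.6.3.3, define TE for QTcB and QTcF actual values as a post-baseline class worse than the baseline class, matching the rule for laboratory grades and vital signs. Keep the upper- and lower-limit rule for HR, PR and QRS, where it fits. Keep the protocol's percentages with QTc above 450, 480 and 500 ms without a baseline condition, and say so in the ECG section.

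The cost is one derivation and the protocol-planned rows. A few more emergent QTc values may be reported.
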